Depression and anxiety worsen musculoskeletal pain and reduce the effectiveness of traditional orthopedic treatments. Nevertheless, addressing mental health is not currently a part of standard treatment for orthopedic conditions. The purpose of this study is to identify strategies to address mental health in the context of orthopedic care in a manner that is feasible, effective, and acceptable to patients and clinicians.

C Study Objectives

C1 Primary Aim

Aim 1: Identify the contextual determinants of implementation success for addressing patients' mental health in the context of orthopedic care.

Using standard qualitative methods, two stakeholder groups will be interviewed: WU orthopedic providers and orthopedic spine patients ≥ 18 years old, with a focus on patients 65 years and older. Using purposive sampling, a goal of at least half of patient stakeholders will be women, and one quarter will identify as an under-represented minority. In semi-structured interviews guided by the Consolidated Framework for Implementation Research (CFIR) and the COM-B model of behavior change, providers and patients will describe needs and preferences related to addressing mental health in a clinical and research context (e.g., recruiting and retaining orthopedic patients in a mental health related randomized controlled trial).

Aim 2: Conduct usability testing for two mental health interventions which can feasibly be implemented in a real-world orthopedic setting: a digital mental health intervention (Wysa) and a novel printed resource guide.

Using semi-structured interviews and the System Usability Scale (SUS), orthopedic patients will participate in an iterative user design process to refine the delivery of Wysa and a printed guide of local and online mental health resources. The printed guide is being prepared as an “enhanced usual care” control intervention for a subsequent R01 randomized controlled trial proposal.^{17,18}

Aim 3: Identify the intermediate mechanisms through which a digital mental health intervention (Wysa) improves mental health symptoms in orthopedic patients.

In a pilot prospective cohort study, patients will receive one month of access to Wysa. Measures of clinical effectiveness (self-reported PROMIS Depression, Anxiety, Pain Interference, and Physical Function¹⁹) and hypothesized behavioral targets (Behavioral Activation for Depression Scale-SF, Chronic Pain Acceptance

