- E-mail will be sent to eligible providers in batches until enough interviews have been scheduled and performed to reach data saturation

- *Verbal consent (waiver of written consent) requested for providers, since they will just be participating in semi-structured interviews.

Patients:

- Prospectively and/or retrospectively review clinic schedules for surgical and non-operative orthopedic spine providers
- To reach purposive sampling goals, some potentially eligible patients may be called prior to appointment date to notify them of the study, assess preliminary interest, and ask to plan staying 60-90 minutes after clinic visit in order to participate in study. Also offer to assist with parking expenses (eg parking validation ticket at CAM).
- Patients will officially be screened at the time of and/or after their orthopedic clinic visit to verify eligibility.
- *Written consent for patients when consent is obtained in clinic. Request the option for verbal consent if the participant is consented over the phone/Zoom.

Contact procedures / permission:

Providers:

- Participants will be e-mailed to be invited to participate.
- They will be asked to complete a brief “demographics” descriptive questionnaire.

Patients:

- Participants will be called or approached in person to be invited to participate.
- During the consent process, they will be asked whether they agree for e-mail and/or text messages to be sent to them. Based on their response, a link to the follow-up REDCap survey will be sent via e-mail and/or text message.

Participants will also be called, e-mailed, and/or text messaged as necessary for reminders to complete the survey.

2.b Randomization Method

No randomization method. No control group.

2.c Risks and Benefits

Risks:

You may experience one or more of the risks indicated below from being in this study. In addition to these, there may be other unknown risks, or risks that we did not anticipate, associated with being in this study.

Although very unlikely, subjects participating in this study may feel inconvenienced from completion of multiple surveys and/or uncomfortable answering some of the survey questions. This risk is minimal because participants will be informed of the estimated time commitment and general content of the survey questions before they consent to participate. The seriousness of this risk is low because participants can withdraw from the study at any time.

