One risk of participating in this study is that confidential information about you may be accidentally disclosed. We will use our best efforts to keep the information about you secure. Please see the section in this consent form titled “How will you keep my information confidential?” for more information.

Benefits:

You will not benefit from being in this study.

However, we hope that, in the future, other people might benefit from this study because information obtained from this study may lead to a better understanding of how to treat patients in an orthopaedic clinic who also experience depression and/or anxiety.

2.d Early Withdrawal of Subjects

If a participant would like to withdraw from this study, they can contact the study coordinator who will document when the patient called to withdraw that their data will not be included in any future data analysis from the time of withdrawal.

2.e Treatment Regimen

After agreeing to participate, patient participants will continue their participation in their orthopedic care plan, as directed by their healthcare provider. We will also assist the participant in downloading the Wysa app to their smartphone or other electronic device, if desired. Through the Wysa app, participants can track and manage their emotions, and they can learn research-based techniques to help them feel better and manage any stress or pain they may be dealing with. Participants will have access to research-based wellness tools such as supportive listening, deep breathing techniques, guided meditation, yoga, and more. Participants can communicate with a virtual artificial intelligence (AI) chatbot, and/or they can message a highly trained and qualified human well-being coach. The intended use of the Wysa app is to encourage mental well-being as an early intervention tool in a self-help context. The Wysa app is considered investigational, which means that it has not been approved by the U.S. Food and Drug Administration.

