Participants will have access to the Wysa app services for one month, and they can use any or all of the services as much or as little as they find useful. No one on the Washington University study team will read participants' chats to the Wysa chatbot. Any chats with a human Wysa well-being coach will remain between just the participant and their coach. The study team will only receive information on whether the participant used the Wysa app, how much they used each feature and/or found it helpful. Participants will be e-mailed and/or sent a text message to the follow-up survey link after one month. The surveys will ask them about their current level of wellness and whether they found the app helpful.

•

2.f Method for Assigning Subjects to Treatment Groups

No control group. Everyone in the provider group, gets the same treatment, and everyone in the patient group will get the same treatment.

E Study Procedures***E1 Screening for Eligibility***

Recruitment of orthopedic provider stakeholders:

Three of the study investigators are faculty members within the WU Department of Orthopaedic Surgery. As such, they have professional and personal relationships with the vast majority of the 70+ orthopedic clinicians and their support staff at WU. These relationships will facilitate a high rate of rapid recruitment from this group of stakeholders into the study. In addition to universal secure, virtual meeting capabilities among this group (Zoom-HIPAA), all orthopedic faculty members have dedicated, secure academic office space in which private semi-structured interviews can be conducted in person.

Recruitment of orthopedic patient stakeholders:

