The study PI ([name]) is one of over 15 spine care subspecialists within the WU Department of Orthopaedic Surgery. She and her colleagues manage patients with a range of sociodemographic backgrounds at multiple clinic sites across the St. Louis metro region including the Barnes-Jewish Center for Advanced Medicine, Barnes-Jewish Hospital Center for Outpatient Health, Barnes-Jewish West County Hospital, and the Barnes-Jewish Center for Advanced Medicine – South County. Furthermore, all of the WU Orthopedics spine patients complete depression and anxiety measures as standard care during each clinical encounter (PROMIS CAT Depression and Anxiety), and [name] research coordinator has specifically enrolled older adult orthopedic patients with spine conditions into mental health related research studies by using these measures as screening items. This patient base and the mental health screening measures will facilitate seamless recruitment of patient stakeholders with a range of self-reported depression and anxiety symptom severity. Additionally, [name] and several other spine providers have adequate clinical space to allow patient rooms to be used for research during clinic hours, and her team has experience recruiting, consenting, and enrolling patients into research studies in person and virtually (via phone or Zoom-HIPAA), from her own clinics and from those of her clinical colleagues. The in-person and virtual participation options will allow patients to participate in the semi-structured interview and usability testing in whichever format is preferred. When convenient for the participant, study recruitment, consent, and the interview can be completed within approximately one hour of the patient's clinical encounter.

E2 Schedule of Measurements

E3 Visit 1

Providers:

- Interviews will occur face-to-face (in a private room) or via Zoom, whichever the participant prefers. Interviews will be audio and possibly video recorded, using WU-HIPAA Zoom technology, handheld audio recorder(s), and/or other similar device. The recordings will be used to transcribe the interview conversation. After the interview, the recording will then be reviewed by a study team member, and all personal identifiers will be removed prior to being uploaded into Rev.com to be transcribed into text for qualitative analysis.

Patients:

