- Suggest that the research places participants or others at a greater risk of harm (including physical, psychological, economic, or social harm) than was previously known or recognized.

5.d Data Collection Procedures for Adverse Events

The research coordinator will document any adverse events reported in a spreadsheet that is password protected and only available to be viewed by the study team.

All adverse events will be reviewed by the principal investigator as they arise.

5.e Reporting Procedures

Events will be reported per the Washington University Institutional Review Board Procedures.

5.f Adverse Event Reporting Period

Events that qualify for immediate reporting described above will be reported within the following timeframe:

- a. 10 working days of the occurrence of the event or notification to the PI or research team of the event.
- b. The death of a research participant should be reported within 1 working day of the occurrence of the event or notification to the PI or research team of the event.

Adverse events/other events that do not require immediate reporting will be provided to the IRB in summary format at the time of continuing review.

F Statistical Plan

F1 Sample Size Determination and Power

No power calculation was performed for this study because the primary aim involves a qualitative analysis. The sample size will be determined by reaching data saturation from the provider and patient stakeholder interviews.

F2 Interim Monitoring and Early Stopping

The Principal Investigator will take responsibility for monitoring patient safety. Patients in the study will be monitored on an as needed basis to assure that they are doing well.

Adverse events will be assessed by [name] to determine if they are serious, unexpected and related to the study procedures.

If a complication should arise, the patient would be previously instructed how to contact the research coordinator.

F3 Statistical Methods

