Interviews will be audio recorded and professionally transcribed. Using inductive and deductive coding approaches based on CFIR and COM-B, a codebook will be developed by one team member, and one or more team members will code all transcripts using NVivo. Group discussion among the research team will be used to resolve coding discrepancies, confirm data saturation has been reached, and organize codes into themes. Scores on the System Usability Scale will be used to iteratively refine both mental health interventions under investigation. Longitudinal PROMIS score changes will be compared between “high” and “low” Wysa users (defined by total Wysa interactions), and associations between changes in behavioral targets (behavioral activation, pain acceptance, sleep quality) and clinical outcomes (depression, anxiety) will be assessed.

G Data Handling and Record Keeping

G1 Confidentiality and Security

Plans to protect the privacy interests of the participants during the conduct of the study:

- 1) Only the minimum necessary private information is collected for the purposes of the study
- 2) Any procedures or interventions conducted as part of the study will be conducted in private setting to the extent possible
- 3) Recruitment/consent will occur in a private setting
- 4) Participants will be able to ask questions in a private setting

Project uses paper and hard copy consents, surveys, data collection forms, research subject binders, or other hard copy materials:

- 1) All materials are stored in secured environment
- 2) Access is limited to research team members only
- 3) Transported securely/shipped with tracking mechanism

Project collects, stores and/or transmits electronic data on mobile devices, desktop computers, servers including cloud servers, email, or any other information in electronic form:

- 1) Password protected
- 2) Access is limited to research team only
- 3) Data in Redcap
- 4) Data in Box
- 5) eCRF system
- 6) Transmitted using recognized security for electronic submission
- 7) Recordings taken during interviews with providers and patients will be reviewed by a study team member, and all personal identifiers will be removed prior to being uploaded into Rev.com to be transcribed into text for qualitative analysis.
- Other

G2 Training

Study coordinator was trained in the Wysa software, and is able to explore the app with the participants in the patient population for use on their own. No formal training is necessary for this study.

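### F3 names no whole-cohort change in PROMIS Depression and Anxiety and no count of patients who worsened; its only group comparison is by self-selected Wysa use, without baseline adjustment

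*Combined protocol and SAP*

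**What the plan says.** All of the quantitative analysis text is in F3 Statistical Methods. Apart from using System Usability Scale scores to refine the interventions, it has two parts. The first is "Longitudinal PROMIS score changes will be compared between “high” and “low” Wysa users", with use defined by total interactions. The second is that associations between changes in the behavioral targets and "clinical outcomes (depression, anxiety) will be assessed".

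The scores have a larger role elsewhere. C1, Aim 3 lists "Measures of clinical effectiveness (self-reported PROMIS Depression, Anxiety, Pain Interference, and Physical Function" among the data taken at baseline and one month, and A2 gives planning data for a later clinical trial as an expected result.

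The design limits what any of this can show. Section 2.b states "No randomization method. No control group". Section 2.e says of participants that "they can use any or all of the services as much or as little as they find useful", and that "patient participants will continue their participation in their orthopedic care plan". E1 describes recruiting "patient stakeholders with a range of self-reported depression and anxiety symptom severity".

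On harm, section 5.d says "The research coordinator will document any adverse events reported in a spreadsheet", and F2 has patients monitored as needed. Neither refers to the PROMIS scores.

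**The concern.** A single-arm month of app access raises a plain descriptive question: did these patients' depression and anxiety scores go up, go down or stay put, and how many patients got worse? The scores to answer it are collected, but F3 does not name the summary.

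Neither named analysis replaces it. Both depend on how patients differ from one another and not on the level of change. The usage contrast has a second weakness. Patients choose how much to use the app during the same month in which the outcome changes, so whatever drives use may also drive the score. F3 states no adjustment, not even for the baseline score.

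At stake is the Aim 3 readout and the planning data drawn from it: the size and spread of one-month change, how often patients deteriorate, and how many one-month scores are missing. B1 reports that the ongoing pilot suggests improvement in orthopedic patients across adult ages. It gives no number who deteriorated and does not describe this spine cohort.

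**Working it through.** The documents state no sample size, SD, usage split, response rate or worsening threshold for these scores, so there is no plan figure to reproduce. The first step is algebra. The later steps use assumed inputs and are illustrations only. Positive change means worsening, and contrasts are high users minus low users.

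**1. A shared shift drops out of both analyses.** Write patient i's change as s + d_i, with s common to all.
- Contrast: (s + mean d_high) − (s + mean d_low) = mean d_high − mean d_low. The term s is gone.
- Association: corr(X, Y + s) = corr(X, Y), and the slope is likewise unchanged.

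**2. What the same contrast can hide.** Assume equal halves with mean changes c − 1 (high) and c + 1 (low), normal with a common SD. The contrast is −2 for every c. The share worsening by at least 5 points is 0.5·P(N(c − 1, SD) ≥ 5) + 0.5·P(N(c + 1, SD) ≥ 5).

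| Cohort change c | High / low means | Contrast | SD 6 | SD 8 | SD 10 |
|---|---|---|---|---|---|
| −3 | −4 / −2 | −2 | 9% | 16% | 21% |
| 0 | −1 / +1 | −2 | 21% | 27% | 31% |
| +3 | +2 / +4 | −2 | 37% | 40% | 42% |

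The group means in the second column separate the three cases. The contrast alone does not. The count does not follow from the means, since it also depends on the spread.

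**3. Self-selection, with a true app effect of zero.** Assume a stable component with SD 6.5 and occasion noise with SD 4.7. Then baseline SD = √(6.5² + 4.7²) = 8.02 and reliability = 42.25/64.34 = 0.657. Split use at the median.
- *Sicker patients use the app more.* Take use = 0.7·(baseline deviation/8) + standard normal noise. Its correlation with baseline is 0.574. The groups then differ at baseline by 2·√(2/π)·0.574·8.02 = 7.35 points, and regression to the mean gives a contrast of −(1 − 0.657)·7.35 = −2.5, an apparent benefit. If less-symptomatic patients use it more, the contrast is +2.5.
- *Recovery for other reasons drives use.* Take a recovery factor worth 1.5 points per SD and the same 0.7 weight. The contrast is 2·√(2/π)·(0.7/√1.49)·1.5 = 1.4 in size: −1.4 if improving patients engage more, +1.4 if struggling patients do.
- *With baseline adjustment*, simulating these four cases, the first pair falls to about 0 and the second stays at ±1.4. Adjustment removes one route of bias and not the other.

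**4. Limits of the proposed summaries.**
- With no mean change, P(N(0, SD) ≥ 5) = 20%, 27% and 31% at SD 6, 8 and 10, so many crossings would be noise or fluctuation.
- At an assumed n of 25, 4 worseners (16%) have an exact 95% CI of 5% to 36%.
- At the same n, the 95% half-width for the mean, t(24)·SD/√25, is 2.5, 3.3 and 4.1 points at SD 6, 8 and 10.

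**The case against.** The strongest reply is that F3 fits its aim. Aim 3 asks about mechanisms, and a usage contrast with change-on-change associations addresses that. Effectiveness is left to a later trial. Comparing changes between groups normally means showing each group's mean, so direction would be visible and a cohort mean could be derived. In a one-paragraph plan, silence on routine descriptive statistics does not rule them out. The proposed count is imprecise, its threshold has no source in the documents, and without a control group it cannot be attributed to the app.

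Much of this stands. The associations are appropriate and not in dispute. A reader might infer that the study could not tell improvement from deterioration. That goes too far, because it holds only if the bare difference is reported, and F3 does not say so. What remains is that F3 does not commit to the group means, and means would not give the count.

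A reader might also infer that the contrast will flatter Wysa. The documents do not support that: they do not say who will use the app more, and the bias can run either way. Nor does F3 draw a causal conclusion from the contrast.

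On safety, the adverse event definition in 5.b is broad enough to include worsening mood, the principal investigator reviews reported events, and patients in a mental health crisis are excluded (D2). So it would be wrong to say that deterioration goes unwatched. But capture depends on someone reporting it, and nothing in the plan looks for it in the one-month PROMIS scores.

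**Conclusion.** The point holds in a limited form. For PROMIS Depression and Anxiety, F3 names a confounded contrast by voluntary use and associations with behavioral targets. It names neither the whole-cohort change nor the number who worsened. That a shared shift cancels is algebra and needs no assumption. Every size given rests on assumed inputs: the 16% to 40% range at SD 8, and biases of 1.4 and 2.5 points in either direction. None of them predicts this study's results.

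A reader might take this as a flaw that undermines the study. It is not. No decision rule depends on these scores, F1 sets the sample size by interview saturation, and the primary aim is qualitative. It is a low-severity, low-cost improvement to the Aim 3 readout and the planning data.

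**What to change.** Add to F3, ahead of the usage contrast:

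> For all patients with both a baseline and a one-month score, regardless of Wysa use, we will report for PROMIS Depression and Anxiety the baseline mean, the mean change with 95% CI, and the number and percentage worsening by at least a threshold fixed before analysis, with an exact 95% CI. We will also report the number lacking a one-month score. Because there is no control group and orthopedic care continues, neither the change nor the count will be attributed to Wysa. For high versus low users we will show each group's baseline score and change, estimate the difference adjusted for the baseline score, and label it descriptive because use is self-selected.

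The threshold is the team's to choose. The 5 points used above is only an example. The baseline mean belongs beside the change because recruitment spans a range of severity, and patients with few symptoms have more room to worsen than to improve.

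The cost is a short paragraph and one small table, with no new visits, items or staff. The downside is wide intervals in a small pilot, and a count that includes measurement noise and natural fluctuation. Baseline adjustment does not remove confounding by other recovery, so the descriptive label is still needed.
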